6.4.7.2 Blood Sample Collection and Handling for Antibody Testing (Serum)

Blood samples for anti-3K3A-APC antibody analysis will be collected from all subjects just prior to receiving the first dose of investigational treatment and again at the Day 14 and Day 30 visits (3 total samples per subject).

Collection:

- Approximately 2-3 mL of blood will be collected into standard clot tubes that do not contain anticoagulant.
- After blood collection, samples will be held at room temperature for at least 20 minutes to allow clotting prior to centrifugation. However please note that samples must be processed within 60 minutes of collection time and divided serum must be stored in a ≤ -70°C freezer within 2 hours of collection time.

Processing:

- To separate serum, blood samples will be centrifuged at 1500 2200 rpm (1500 x g) at 2°-8°C for 10-15 minutes.
- The serum will be removed from the blood, split into 2 equal aliquots, and stored in 2 mL labeled Cryotube[™] containers.

• Serum will be immediately placed in a temperature-controlled (with recordings) and alarmed ≤ -70°C freezer within 2 hours of collection.

NOTE: Subjects unable to return to the study site may have blood drawn at an outside medical facility or at home. Serum collected outside a medical facility may be placed in a wet ice slurry for 2-3 minutes and centrifuged at room temperature at 1500 - 2200 rpm (1500 x g) for 10-15 minutes. After aliquoting, the serum must be placed on dry ice for transport or shipping to the study site.

Storage:

• Samples will be stored in $a \le -70^{\circ}$ C freezer at the Investigational site.

Shipping:

 Frozen samples will be batch shipped on dry ice to the central laboratory at the University of Rochester for storage. Pre-printed air bills and temperature-validated packaging will be provided by the central laboratory. Primary and back-up aliquots should always be shipped separately in order to mitigate against loss. Refer to the 'Laboratory Manual' for additional detail on the shipping frequency of samples.

Analysis:

Antibody analysis will occur at Antibody analysis will occur at A qualitative enzyme-linked immunosorbent assay (ELISA) method has been developed and validated by For anti-3K3A-APC antibody detection. Samples collected for anti-drug antibody analysis will only be used for antibody-related analysis and method development.

6.4.8 Questionnaire Certification

Investigators and designated study staff will be trained and certified to use the NIHSS and the mRS, using a recognized certifying agency.

6.4.9 Imaging Central Review

A central reader will review all scans for each subject who receives at least one infusion of study drug. Five scans per subject are expected, including two standard of care scans and three study mandated scans. Please refer to the 'Imaging Plan' for details.

7 MANAGEMENT OF ADVERSE EXPERIENCES

Expected AEs due to stroke can be estimated from the Virtual International Stroke Trials Archive (VISTA)⁴⁹. In the VISTA dataset, 5775 placebo-treated patients were analyzed. One-hundred-thirty-two (132) of 756 types of AEs accounted for 82.7% of reported events. Thirty-five (35) of the most common types of SAEs are listed below:

Stroke in evolution	11.2% ¹
Pneumonia	5.6%
Ischemic cerebral infarction	4.8%
Brain edema	4.3%
Cardiac failure	3.4%
ZZ-3K3A-201	
Version 8.1 Final	
Version date 7-Oct-2016	

Myocardial infarction	2.9%
-----------------------	------

- Cerebral hemorrhage 2.5%
- Aspiration pneumonia 2.5%
 - Respiratory failure 2.2%
 - Hemorrhagic transformation2.2%Pulmonary embolism2.0%
- Pulmonary embolism2.0%Atrial fibrillation1.8%
- Urinary tract infection 1.7%
- Pulmonary edema 1.5%
- Cerebrovascular disorder 1.5%
- Cardiac arrest 1.5%
- Carotid artery disease 1.4%
- Sepsis 1.3%
- Angina pectoris 1.2%
- Hypotension 1.1%
- Coma 1.1%
- Pyrexia 1.1% Renal failure 1.0%
- Headache 0.9%
- ICP increased 0.9%
- Respiratory tract infection 0.9%
- Bradycardia 0.8%
- Transient Ischemic Attack
- Hypertension0.8%Hemorrhagic Cerebral Infarction0.7%Somnolence0.7%Cerebral Incarceration0.6%
- Cerebral Incarceration Deep vein thrombosis Syncope
- Depression 0.5%

¹Shown as percentage of total SAE occurrence; 53 types of SAEs in total were identified.

0.8%

0.6%

0.5%

Bacterial pneumonia is one of the most common causes of death in acute stroke patients. Reduction of bulbar reflexes, drowsiness, dysphagia, and subsequent aspiration are considered to be major contributors to the high incidence of bacterial pneumonia after stroke.⁵⁰ Recent studies in patients with moderate to severe stroke found pneumonia rates between 10.7 and 21%.⁵¹⁻⁵³ Whether or not the increase in pneumonia rate affects 3-month outcome after stroke is controversial.⁵⁴ Symptomatic ICH occurs in about 6% of patients treated with tPA¹³.

8 STATISTICAL CONSIDERATIONS

The NeuroNEXT Data Coordinating Center will develop a Statistical Analysis Plan (SAP) in collaboration with the protocol principal Investigator and protocol steering committee.

8.1 General Design Issues

8.1.1 Summary of Study Design

This is a multicenter, prospective, randomized, controlled, double-blinded Phase 2 study intended to evaluate the safety, PK, and preliminary efficacy of 3K3A-APC following administration of tPA, or mechanical thrombectomy or both, in patients with moderate to severe acute ischemic stroke. The original version of the CRM method proposed enrolling one subject at a time⁵⁵. However, others have shown that the performance of the CRM may be improved by enrolling cohorts instead of a single subject¹. Correspondingly, this study will utilize a modified version of the CRM in order to establish a MTD.

The study will enroll approximately 115 subjects, which includes the planned 88 subjects in groups of four (each cohort will include one placebo and three treated subjects) and the additional placebo subjects who may be enrolled during safety review pauses. While placebo is not needed to determine the MTD, a placebo group has been included in order to conduct secondary analyses to examine for a reduction of pre-clinical tPA/mechanical thrombectomy-related bleeds by central read (it is predicted from studies that treatment reduces thrombolysis-related petechial hemorrhage). Subjects will not be considered part of the intent-to-treat (ITT) cohort until they receive any amount of 3K3A-APC or placebo. For example, 'Early Responders,' subjects whose symptoms resolve between initial randomization and initiation of IMP infusion such that they are no longer eligible (repeat NIHSS <5), will be removed from the study and replaced. At any time if enrollment is so rapid that two consecutive cohorts are awaiting DLT review, the IWRS will randomize any enrolled patients to placebo so as to preserve site-level blinding and trial enrollment momentum. These extra placebo treated subjects will enhance the power to detect a change in bleed rates for 3K3A-APC-treated subjects.

Following completion of tPA infusion or initiation of mechanical thrombectomy (arterial puncture), whichever occurs sooner, eligible adult subjects will receive 3K3A-APC or placebo 30 to 120 minutes later given as a 15-minute infusion. Subjects will receive another 15-minute infusion of 3K3A-APC every 12 hours (+/- 1 hour) for up to 5 total infusions. Four dose levels will be considered for this study: 120, 240, 360, and 540 µg/kg. For the purposes of this study, we assume an established background symptomatic intracerebral hemorrhage (SICH) rate of 3-6%²⁻⁷. Correspondingly, the MTD will be defined as the highest dose with a DLT rate of 10% or less. Subjects will be enrolled to 3K3A-APC dose cohorts in groups of four (three to specified treatment

dose and one to placebo). Subjects will generally be enrolled at the dose estimated from the assumed dose-response model and prior data to be closest to the MTD. However, the initial cohort will start at the lowest dose level ($120 \mu g/kg$) and the dose level may be escalated by no more than one dose between consecutive cohorts (there are no restrictions on dose level de-escalation). Intra-subject dose modification is not permitted during the study.

Prior to starting the CRM, based on a best estimate from the literature and previous studies, the four dose levels will be assigned prior probabilities as indicated in Table 3 below.

Table 3. Assumed prior probabilities of toxicity at four dose levels considered for the study:

Dose Level	120	240	360	540
Prior Probability of Toxicity	5%	7%	9%	11%

When designing a CRM, O'Quigley, Pepe and Fisher recommend using a single-parameter doseresponse model $\psi(x_i^*, a)$, which is probability of toxicity at dose x_i^* for some unknown parameter, a, which defines the shape of the dose-toxicity function. For this study, a hyperbolic tangent doseresponse model will be used, in which

$$\psi(x_i^*,a) = \left\{\frac{\tanh(x_i^*+1)}{2}\right\}^a.$$

After each group of subjects has been treated, and their status observed as to whether or not each had a DLT, the posterior mean of *a* will be calculated. Based upon that estimate, \hat{a} , the highest dose with estimated toxicity probability, $\psi(x_i^*, a)$ less than or equal to 10% will be allocated to the next group of subjects needing treatment assignment. If this dose is more than one level higher than the previous dose allocated to a cohort, the dose will only be increased one level. After the final group of subjects is enrolled, the final MTD will be defined as the highest dose with estimated toxicity probability less than or equal to the target toxicity level of 10%.

Hence, the design will proceed as follows:

- Enroll the first 4 subjects into cohort 1.
 - Treat one of the four subjects (chosen randomly) with placebo.
 - $_{\odot}$ Treat the other three subjects with the lowest dose: 120 µg/kg.
 - Observe the number of subjects (out of the three treated subjects) that have a DLT per study definition. Any given subject who receives only one dose of study drug and does not experience a DLT will not be included in the CRM calculation (i.e. two or more doses will need to be administered to be included).
 - Based upon the observed information from the three treated subjects, refit the assumed dose-response curve.
- Initially (through version 7.1. of the protocol), the re-estimated dose-response curve using all cohorts enrolled to date was then used to determine the highest dose level of the four under consideration that has an estimated probability of toxicity less than or equal to 10%

- The next cohort of subjects is treated at the dose level specified above unless the chosen dose level is more than one level higher than the current level. If so, treat the next cohort of subjects at the next dose level above the current level.
- Based on a DSMB recommendation, this process was changed as of version 8.0 of the protocol. The basic process proceeds as described above, but once all subjects in a given cohort (n) have been enrolled, data from all prior cohorts (cohort 1, cohort 2,, cohort n-1) are used to determine the dose level of cohort n+1.
 - If enrollment is rapid such that both cohort (n-1) and cohort (n) are filled and awaiting DLT review, new subjects enrolled will be randomized to placebo until cohort (n-1) has been reviewed. (For example, if both cohort 13 and 14 are filled and awaiting review, subjects will be randomized to placebo until cohort 13 is closed and the model is rerun to determine the dose for cohort 15.)

The MTD will be defined as the dose that would be chosen from the CRM at the final step. The study will stop once the first of the following criteria have been met:

- The maximum number of cohorts (22) has been observed.
- If at any time after half of the cohorts (11) have been observed, two consecutive iterations suggest a 15% or higher toxicity rate at the lowest dose (stop for safety)
- If the study proceeds straight to the highest dose, and then observes 9 successive cohorts at the highest dose with no observed toxicity (stop and declare highest dose the MTD)

Through simulation it was determined that it would be extremely unlikely to observe no DLTs after 9 successive cohorts if the true toxicity rate were 10%. Thus, after 9 cohorts we would have sufficiently determined that all doses under consideration are safe and stopping early would be justified.

Non-serious adverse events (AEs) will be collected through actual Day 7. More specifically, subjects will be evaluated for DLTs from administration of the first dose to 48 hours following the last dose of study treatment. Blood samples for PK will be collected from approximately 40 subjects at a sub-set of study sites following one of the doses of 3K3A-APC at the following time points: end of infusion and 20, 40, 60 and 80 minutes after the end of infusion. Subjects must be seen for assessments on Days 7, 14, 30 and 90. MRI scans, including SWI sequences, will be obtained at 7, 30 and 90 days after stroke.

A SRC will review the safety data for each potential DLT, and make a final determination as to whether or not an incident should be classified as a DLT. Assignment of the dose for a cohort will not occur until all potential DLTs have been reviewed by the SRC..

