NOTE: All suspected DLTs will be reviewed by a Safety Review Committee, and those reported DLTs that are considered possibly related to study drug but definitely related to another event will not be considered DLTs upon final adjudication. An example of such an event would be an elevated aPTT following dose 1 in a subject who undergoes mechanical thrombectomy during which heparin is administered; the elevated aPTT can be attributed to the heparin and therefore should NOT be considered a DLT in this isolated instance. Another example would be the occurrence of hypofibrinogenemia in a subject who receives tPA. Low fibrinogen levels can be attributed to tPA, and there is a documented rate of occurrence of 11% in subjects receiving tPA⁸. Furthermore, 3K3A-APC does not cause a reduction in the level of fibrinogen in plasma and therefore this finding should NOT be considered a DLT.

Should a subject experience a DLT, dosing of study treatment should be discontinued as soon as the Investigator becomes aware of the event.

3.1.2 Safety Review Committee:

An independent Safety Review Committee (SRC) will be formed and charged with reviewing and adjudicating DLTs in order to objectively inform the CRM as described in section 8.1.1. The SRC will be comprised of a committee chair, the IMM and three qualified participants, as outlined in the 'Safety Review Committee Charter.' Should a DLT be reported or suspected, the DCC will notify the SRC, which will be convened to review the AE(s). If a DLT is confirmed by the SRC, the NeuroNEXT statistics group will be informed so that the safety event can be fed into the CRM and the dose level determined automatically by the model for the next cohort needing a treatment level assignment. The SRC will be responsible for final determination of whether a particular event will be classified as a DLT, but will not participate directly in dose selection. Refer to 'Safety Review Committee Charter' for details.

3.1.3 Data Monitoring and Data Safety Monitoring Board:

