Four dose levels will be considered for this study: 120, 240, 360, and 540 µg/kg. Following completion of tPA infusion, or initiation of mechanical thrombectomy (arterial puncture), whichever is sooner, eligible adult subjects will receive 3K3A-APC or placebo 30 to 120 minutes later given as a 15 minute infusion. Subjects will receive another 15 minute infusion of study treatment every 12 hours (+/- 1 hour) for up to 5 total doses (or until discharge, whichever occurs first). It is preferable not to skip doses of study drug, and should a dose need to occur outside of the +/- 1 hour window (which will be reported as a protocol deviation), doses should never be given within 8 hours of one another.

For the purposes of this study, we assume an established background symptomatic intracerebral hemorrhage (SICH) rate of 3-6% (Wahlgreen et al, 2007; Hacke et al, 2008; Berkhemer et al, 2015; Campbell et al, 2015; Goyal et al, 2015; Saver et al, 2015). Correspondingly, this study aims to identify the highest dose with a DLT rate of 10% or less. Subjects will be enrolled to 3K3A-APC dose cohorts in groups of four (three to specified treatment dose and one to placebo). Subjects will generally be enrolled at the dose estimated from the model at that time, based on the assumed original dose-response model and all prior observed data to date, as the highest dose with a DLT rate of 10% or less. However, the initial cohort will start at the lowest dose (120 µg/kg) and the dose level may be escalated by no more than one dose between consecutive cohorts (there are no restrictions on dose level de-escalation). Intra-subject dose modification is not permitted during the study. After the final group of subjects is enrolled, the final MTD will be defined as the highest dose with an estimated toxicity probability less than or equal to the target toxicity level of 10%.

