Much of the process for implementing the selection of dose for each subsequent cohort of subjects has been automated. Once the DLT status for all evaluable subjects in a cohort is complete, the IWRS will notify both statisticians via email that a new cohort is available for analysis. At that point, the primary statisticians will independently complete the dose recommendation process. The statistician who submits the initial dose recommendation will be referred to as the initial statistician, while the statistician who submits the dose recommendation second will be referred to as the validation statistician. The initial statistician will enter the production database and save the table of DLTs for each cohort as a SAS table, to ensure that each dose recommendation can be reproduced at any time during or after the conduct of the study. In parallel fashion, both the initial and validation statisticians will run a SAS program that details the selection of the next dose and enter their selected dose for the next cohort of subjects into the study website. Once both statisticians enter the next dose recommendation and provided the two recommendations match, the randomization table will re-open and participants will be randomized to the newly recommended dose or placebo in a 3:1 ratio. If the two doses do not agree, the IWRS notifies the statisticians of a dose match error via email, and the process is repeated until a new dose recommendation is verified for the next cohort.

A list of backup statisticians will also be maintained. These individuals should be capable of serving in this capacity if either or both of the primary statisticians are unable to perform the tasks outlined below. It is the responsibility of the primary statisticians to place the backup statisticians 'on call' should the primary statisticians know of an upcoming period of unavailability.

Final CRM results will be displayed, by cohort, in the following format:

Table 2. CRM Cohort Toxicity Estimates

Cohort	Selected Dose (µg/kg)	# of Evaluable Subjects	# of DLTs	Toxicity Estimates			
				120 (µg/kg)	240 (µg/kg)	360 (µg/kg)	540 (µg/kg)
Priors							
1	120	X	X	XX.X%			
2	XXX	X	X	XX.X%			
...			
22	XXX	X	X	XX.X%			

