10.6 Safety Review Committee

An independent Safety Review Committee (SRC) will be formed and charged with reviewing and adjudicating DLTs in order to objectively inform the CRM. The SRC will be comprised of a committee chair, the IMM, and three qualified participants – as outlined in the 'Safety Review Committee Charter'. For every reported DLT, the SRC will review the event and make a final determination as to whether or not an incident should be classified as a DLT. The SRC's final adjudication (DLT = yes/no) will be recorded using the DLT Adjudication Form as part of the IMM Evaluation Module. Assignment of the dose for the following cohort will not occur until all four subjects in a cohort have completed the Day 8 assessment and all potential DLTs have been reviewed by the SRC. The SRC will be responsible for final determination of whether a particular AE will be classified as a DLT, but will not participate directly in dose selection. On a quarterly basis, the SRC will also review the same aggregate reports viewed by the IMM (see section 10.5).

If in the extraordinarily unlikely event the Central Reader identifies a new suspected DLT that was not previously recognized for that subject, the Central Reader will inform the PPI who will contact the DCC to initiate the AE/DLT review process so that the DLT can be adjudicated by the SRC.

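### Under the lag rule, cohort n+1 can be dosed above the level at which cohort n has already had a confirmed DLT, and no text bars it

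*Protocol*

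**What the plan says.** The lag rule appears in Protocol 3.1, Protocol 8.1.1 and SAP 7. It is presented as a DSMB-recommended change from version 8.0: once cohort n is enrolled, data from cohorts up to "cohort n-1) are used to determine the dose level of cohort n+1". The worked example is explicit: with cohorts 13 and 14 both full, "subjects will be randomized to placebo until cohort 13 is closed and the model is rerun to determine the dose for cohort 15".

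The only limit on going up is that "the dose level may be escalated by no more than one dose between consecutive cohorts". The SRC adjudicates DLTs but has no direct part in choosing doses (Protocol 3.1.2; SAP 10.6).

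Four other current passages do not mention the lag:

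- Protocol 3.1.2: the statistics group is told of a confirmed DLT "so that the safety event can be fed into the CRM and the dose level determined automatically by the model for the next cohort" that needs an assignment.
- SAP 1: the dose is generally the one estimated "based on the assumed original dose-response model and all prior observed data to date".
- Protocol 8.1.1, at its end: "Assignment of the dose for a cohort will not occur until all potential DLTs have been reviewed by the SRC".
- SAP 10.6: "Assignment of the dose for the following cohort will not occur until all four subjects in a cohort have completed the Day 8 assessment", with SRC review also finished.

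On timing, the lag sentence ties the step to cohort n being fully enrolled. SAP 7 describes a different trigger: "Once the DLT status for all evaluable subjects in a cohort is complete, the IWRS will notify both statisticians via email", and the statisticians then run the model. SAP 7 also says that the final MTD comes from a last model run on all observed data.

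**The concern.** The lag exists so that dosing need not wait for pending results. As written it also discards results that are no longer pending. If a cohort n subject has a DLT, possibly a symptomatic intracranial hemorrhage, and the SRC confirms it before the cohort n+1 dose is set, the model does not see it. The model may then recommend the next level up, and the one-level cap allows that.

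Nothing automatic prevents this. SAE reporting, review by the Independent Medical Monitor (IMM) and notice to the DSMB chair let someone intervene, but none of them blocks the assignment. At stake is the exposure of the three treated subjects in cohort n+1, in a trial whose primary objective is safety. The unreconciled passages make it harder to know what was intended.

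**Working it through.** **Inputs.** Prior DLT probabilities s = 5, 7, 9, 11% at 120, 240, 360, 540 µg/kg; 10% target; three treated subjects per cohort; 22 cohorts; one-level cap; both early-stopping rules (Protocol 8.1.1, SAP 7). Planned accrual is 0.3 × 15 = 4.5 subjects per month (Protocol synopsis).

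**Assumptions not in the documents.** The prior on *a* is exponential with mean 1, checked against a lognormal with variance 1.34. The lowest dose is used when no dose qualifies. The lag starts at cohort 13, inferred from the worked example. DLT status is known at Day 8 plus 0 to 7 days.

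**Model.** With the SAP form of the curve, the DLT probability at dose i is s_i^a, evaluated at the posterior mean of *a*.

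**The plan's own figures first.** Correct selection in Table 5, scenarios 1-6:

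| | Table 5 | Reproduced |
|---|---|---|
| Unlagged | 91/68/32/42/54/61 | 91/69/31/45/53/61 |
| Lagged | 88/67/31/42/54/61 | 91/69/31/43/52/60 |

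The match is within 3 points when the dose closest to 10% is chosen. The written rule (highest dose at or below 10%) fits less well, so the ranges below cover both rules.

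**A reachable path under the written rule.**

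| Cohorts | Dose | DLTs |
|---|---|---|
| 1, 2, 3 | 120, 240, 120 | 0/3, 1/3, 1/3 |
| 4-8 | 120 | 0/15 |
| 9-10 | 240 | 0/6 |
| 11-12 | 360 | 0/6 |
| 13 | 360 | 1/3, confirmed |

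- After cohort 11 the estimate at 540 is 10.5%, so cohorts 12 and 13 receive 360.
- Cohort 14 under the lag uses cohorts 1-12: 1/21 at 120, 1/9 at 240, 0/6 at 360. The posterior mean of *a* is 1.061, and 0.11^1.061 = 9.6% at 540. Cohort 14 goes to **540**.
- With cohort 13 counted, the posterior mean is 0.959. Then 0.11^0.959 = 12.0% at 540 and 0.09^0.959 = 9.9% at 360. Cohort 14 stays at **360**.

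The lognormal prior gives the same doses at every step.

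**Can confirmation come in time?** At 4.5 per month, the first subject of a cohort enrols about 3/4.5 = 0.67 month, or 20 days, before the fourth. That is longer than Day 8 plus 7 days. At 9 per month the gap is about 10 days. In simulation at planned accrual, 26-47% of cohort n DLTs are confirmed when the n+1 dose is set, if it is set when cohort n fills.

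**Trials with at least one escalation above the dose of a confirmed cohort n DLT (range over scenarios 1-6).**

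| Setting | Share of trials |
|---|---|
| No lag | 0% |
| Lag from 13, 4.5/month, dose set when cohort n fills | 1-15% |
| Same, lag from 10 or 16 | 1-18% |
| Lag from 13, 6/month, Day 8 plus 7 | 0.4-6% |
| Lag from 13, 9/month | 0.3-4% |
| Dose set when cohort n-1 closes | 0% |
| Lag from 13, every cohort n DLT already confirmed (upper bound) | 4-28% |

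The 0% for the cohort n-1 trigger follows by construction from one common review delay: cohort n enrolled later, so none of it can be confirmed first. With unequal delays it would be near zero rather than exactly zero. Escalation above a cohort with two or more confirmed DLTs occurs in 0-0.9% of trials with the lag from cohort 13.

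**The case against.** The lag is a specific, dated change that the DSMB recommended, with a worked example, and it is repeated consistently. The sponsor simulated it and accepted its cost. All of that stands, and it is why the lag should stay. It also limits several stronger readings.

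- **That four passages contradict the lag.** Only Protocol 3.1.2 and SAP 1 bear on which data enter the model. SAP 1 is qualified as the general case, and Protocol 3.1.2 refers to the next cohort that needs an assignment, which can fit the lag. The end of Protocol 8.1.1 and SAP 10.6 govern when review must finish. SAP 10.6 says only a cohort, which can be read as n-1. The gap is lack of reconciliation, not outright conflict.
- **That subjects could be dosed on two divergent readings.** SAP 7 requires the two statisticians' doses to match before randomization reopens. A mismatch repeats the process.
- **That the event is common.** Rates of 11-49% arise only if the lag runs throughout the trial. Here it began at version 8.0, after unlagged cohorts. The plan also expects about 115 - 88 = 27 extra placebo subjects, against 18.2 in simulation with the lag from cohort 13 and Day 8 plus 3 days. That suggests faster accrual or slower review. The 6/month run gives 32 extra placebo subjects and only 0.4-6%.
- **That the lag puts more subjects on toxic doses overall.** Table 5 shows fewer at 540 under the lag in scenarios 3-6: 20.9 v 23.6, 11.1 v 12.1, 3.8 v 4.8 and 1.3 v 1.9.

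None of this closes the narrower gap. Table 5 reports selection and allocation, not escalation above a confirmed DLT, and no sentence prevents it.

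**Conclusion.** The concern holds as a narrow safety gap. The written lag rule permits escalation above the dose of a DLT already confirmed in cohort n, and the example shows that the path is reachable under the stated rule with either prior. The breach in that example is modest: an estimate of 12.0% at the assigned dose against a 10% target.

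The frequency cannot be fixed from the documents. It depends on the prior on *a*, the cohort at which version 8.0 took effect, accrual, the confirmation delay and, above all, which trigger sets the dose. The lag sentence supports cohort n filling (about 1-15%). The automated step in SAP 7 supports cohort n-1 closing (near 0%).

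A reader might infer that the MTD estimate is compromised. It is not, because the final run uses all observed data. The effect falls on subjects in cohort n+1. Given the small cost of closing the gap, it should be closed.

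**What to change.** Keep the lag. Add to Protocol 3.1, Protocol 8.1.1 and SAP 7:

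> *Cohort n+1 is not assigned a dose above cohort n's dose if, when the dose is set, cohort n has an SRC-confirmed DLT or a suspected DLT awaiting SRC adjudication.*

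Align Protocol 3.1.2, the end of Protocol 8.1.1, SAP 1 and SAP 10.6 with the lag, naming cohort n-1 as the cohort whose review must be complete.

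Do not feed partial cohort n data into the model. DLT-free subjects need only the IMM's review, whereas suspected DLTs also need the SRC. DLT-free subjects could enter first and tilt the estimate towards escalation. That option would need simulation with separate delays for the two groups.

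Cost: one sentence in three places, four aligned passages and one check in the dose-selection program. With the bar alone, the lag in force throughout and every cohort n DLT treated as known, such escalations fall to 0%. Correct selection in scenarios 1-6 moves from 88.8/68.6/30.6/41.1/52.2/61.1% to 88.1/68.4/30.7/40.2/52.1/60.0%, at most 1.1 points. Mean DLTs per trial fall by 0.1 or less. The bar changes the dose and not when it is set, so it needs no extra placebo subjects. The downside is slightly slower escalation, including an occasional one-cohort hold for a suspected DLT that the SRC later rejects, which was not simulated.
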